### 3. Research Procedures (Figure 2)

1) Obtaining signatures on the consent form at screening visit.

The PI and the POC will follow the protocol in the approved IRB application while we are obtaining signatures from the potential subject. The information will be given to the potential subject in the separate room. The potential subject will be encouraged to ask the PI and the POC any questions regarding this protocol. (Approximately 40 to 60 minutes)

2) Placement of a mini-screw at the buccal plate of the extraction socket in one side (left or right) one week after the atraumatic extraction of maxillary premolars

- Limited volume CBCT with high resolution will be exposed before the mini-screw placement; this is standard of care.
- Clinical photographs and intraoral images will be obtained for both sites.
- One mini-screw (8 mm length) will be placed at the buccal plate of one extraction site. After bone sounding, a mini screw will be placed at the position 3 mm from the alveolar crest. The other extraction site will be untreated. (Approximately 30 minutes)
  - The PI and the POC will monitor subjects closely.
  - Local anesthesia with lidocaine will be administered to minimize patients' discomfort.
  - Postoperative instruction will be given to subjects.

3) 3 months follow-up (30 minutes); Clinical photographs and intraoral images will be obtained for both sites.

[figure not shown]
4) 6 months follow-up (40 minutes)

- The mini-screws will be removed.
- Clinical photographs and intraoral images will be obtained for both sites.
- Limited volume CBCT with high resolution will be exposed; this is a study procedure.

**Figure 2.** Intraoperative photographs from one of subjects. (a) Mini-screw (arrow) placed 1 week after extraction. (b) 3-month follow up. (c) 6-month follow up after removal of screw.

**4. Radiographic Measurements:** CBCT will be exposed after teeth extraction and before the mini-screw placement ( $T_0$ ). One mini-screw will be placed at the buccal plate of the extraction socket one week following the extraction of maxillary premolars in one side. The other extraction socket site will be untreated. At 6 months, the follow-up CBCT will be exposed for the maxilla after removal of the mini-screws. A blinded evaluator will measure the width of alveolar ridge on the CBCTs made at  $T_0$  and  $T_6$ . Changes in the width of alveolar ridge were measured from the outer wall at  $T_0$  to the outer wall at  $T_6$ . A positive value indicates bone loss. In the sagittal section, three levels will be determined by measuring from the crest to the apex and dividing the socket length into thirds. The measurements will be performed in coronal and axial sections (Figs 3a and 3b).

**Figure 3.** Measurements of bone loss after tooth extraction on CBCTs. (a-b) Examples of coronal (a) or axial (b) measurements. Changes of bone level from  $T_0$  to  $T_6$  was measured. Superimposition of two CBCT images ( $T_6$ , blue;  $T_0$ , grey) was performed using Invivo 6.0 software. Right side images present magnification of insets in left panels. (c-d) Changes in the width of alveolar ridge (mean  $\pm$  SD) in the experimental (exp) and the control (con) side at the crestal (C), middle (M), and apex (A) level in coronal or axial sections.

**5. Interim data and statistical analysis:** No inflammation and infection related to the mini-screw placements were observed in all 6 subjects. Miniscrews were removed at 6 months from 3 subjects and at 8 months from 3 subjects (the mean of 7-month) in keeping with planned dental treatments. Overall, the experimental side with the miniscrew placement showed less bone loss than the control side at the crestal, middle, and apex level in both coronal and axial measurements (Figs 3c and 3d). Upon completion of the study, a paired t-test will be performed to compare the changes in the width of alveolar ridge from the two sides. We will also measure mineral density distribution at the extraction sites from the two sides using CBCTs.

**6. Expected outcomes:** We predict that the experimental side with mini-screw placements will exhibit a significantly less bone loss than the control side. Bone density in the experimental side will be significantly greater than the control side.

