## Abstract

The remodeling of the alveolar bone following tooth extraction results in significant bone loss at the extraction site. An excessive bone loss hampers the implementation of treatment plans, prediction of esthetic outcomes, and patient satisfaction. Placing bone substitute materials in an extraction socket may reduce the alveolar bone resorption. However, postoperative infection and inflammation are common side effects following bone graft surgeries. Finding a less invasive approach to preserve the alveolar ridge would be amenable to dental clinic. An animal study reported that bone density significantly increased in the extraction site with transcortical mini-screw placements, exhibiting markedly less atrophied alveolar ridge. In addition, the side effects from a mini-screw placement are minimal and no antibiotics are required. Therefore, we propose the placement of a transcortical mini-screw at the buccal plate of an extraction socket as a minimally invasive approach to preserve the alveolar ridge. The objective of this study is to determine the effects of transcortical mini-screws placed at the buccal plates of the extraction sockets in humans. We hypothesize that placement of a transcortical mini-screw at the buccal plate will significantly reduce bone loss at the site. To test this hypothesis, we are performing a prospective split-mouth design study. We are recruiting patients who need extraction of two maxillary premolars for orthodontic treatments. Cone beam computed tomography (CBCT) is exposed after the extraction of two premolars and before a transcortical mini-screw placement ( $T_0$ ). One 8-mm length mini-screw is placed at the buccal plate of the extraction socket on one side. The contralateral extraction socket is untreated. The mini-screw is removed at 6 months and the follow-up CBCT is obtained ( $T_6$ ). We will compare changes in the alveolar bone width at both extraction sides using the CBCTs. We predict that the placement of a transcortical mini-screw at the buccal plate of the extraction socket significantly reduces bone loss at the extraction site. Results of this study will offer a useful measure to sustain an edentulous alveolar ridge for a lengthy period without losing bone proper.

[figure not shown]

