## **SPECIFIC AIMS**

Specific Aim 1: To evaluate the clinical outcomes between the treated sites with a transcortical screw (the experimental group) and the non-treated sites (the control group)

*Null Hypothesis:* There will be no differences in clinical parameters between the two groups.

*Approach:* The investigators will conduct a prospective split-mouth design clinical study. The investigators will compare the clinical changes in the vertical ridge height and the horizontal ridge width at 3 months and 6 months from baseline (tooth extraction).

Specific Aim 2: To evaluate the radiographic outcome between the experimental and the control group

*Null Hypothesis:* There will be no difference in alveolar bone height and width between the two groups.

*Approach:* The study will measure the alveolar bone heights and widths using cone beam computed tomographies (CBCTs) at baseline and 6 months.

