## **APPROACH**

This is an on-going prospective clinical study under a protocol approved by the IRB (HP-00076020). Six subjects completed the study protocol. Interim data analysis was performed from these six subjects.

1. Sample size determination: The original sample size was determined to provide 80% power to recognize a significant difference of 1 mm between the two sides with a 95% confidence interval ( $\alpha=0.05$ ) and standard deviation of 1.0 mm, considering the difference in the mean width of the edentulous alveolar ridge as the primary outcome variable. Based on the power analysis reperformed by following the formula described by Faul et al using the interim data from the 6 subjects, 14 subjects will provide 80% power to recognize a significant difference of 0.5 mm in the width of the alveolar ridge between the two sides.

2. The Study Population: Patients with the following conditions are included: a) age  $\geq 18$  years, and b) two maxillary premolars (one from the left side and the other from the right side) required to be extracted in accordance with recommended dental treatment plans. Exclusion criteria are as follows: a) hyper-/hypothyroid dysfunctions, b) diabetes mellitus, c) subjects with a history of a chronic use of corticosteroid ( $> 6$  months), d) subjects with a history of taking oral/IV bisphosphonates within the past 2 years, e) smokers, and f) other systemic conditions influencing bone integrity.

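### No method is stated for choosing which socket receives the mini-screw, and neither randomisation nor concealment is mentioned, so the paired comparison is open to side-selection bias in either direction

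*Combined protocol and SAP*

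**What the plan says.** The choice of side is described in three places, none with a rule.

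- Abstract: "One 8-mm length mini-screw is placed at the buccal plate of the extraction socket on one side"; the opposite socket is left untreated.
- Approach, 3. Research Procedures, item 2): the step is headed "Placement of a mini-screw at the buccal plate of the extraction socket in one side (left or right", and the detail beneath adds "One mini-screw (8 mm length) will be placed at the buccal plate of one extraction site".
- Approach, 4. Radiographic Measurements: again one side is treated, with no word on how it is picked.

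Specific Aim 1 gives the design: "The investigators will conduct a prospective split-mouth design clinical study". On the order of events, item 2) says: "Limited volume CBCT with high resolution will be exposed before the mini-screw placement".

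The one stated protection against bias is in 4. Radiographic Measurements: "A blinded evaluator will measure the width of alveolar ridge on the CBCTs". For the analysis, 5. Interim data and statistical analysis plans that "a paired t-test will be performed to compare the changes in the width of alveolar ridge from the two sides", with no adjustment for baseline width or side. The Sample size paragraph says that "14 subjects will provide 80% power to recognize a significant difference of 0.5 mm".

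**The concern.** In a split-mouth trial, chance assignment of the side is what allows a difference between the two sockets to be attributed to the treatment. Without it, the within-patient difference is the screw effect plus the effect of whatever decided the side.

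The sequence written into the plan leaves room for that decision to be informed, because both sockets have been imaged before one is treated. An operator could prefer the socket with the sounder buccal plate, which would probably have lost less bone anyway; the result would flatter the screw. An operator could equally prefer the socket that seems to need help, which would hide a real effect and cost power. Nothing in the documents says which is more likely.

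The stated safeguards act elsewhere. Blinding protects the measurement of width, not the choice of socket. Pairing removes differences between patients, not differences between one patient's two sockets. With a target of 0.5 mm and 14 subjects, a modest imbalance can matter.

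**Working it through.** The omission is established by reading. The arithmetic only shows how much it could matter.

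**Inputs from the documents** (Sample size paragraph): n = 14, 80% power, a difference of 0.5 mm, α = 0.05. Sidedness is not stated; two-sided is assumed. The interim SD behind the 14 is not given, so that figure cannot be reproduced independently, but the SD it implies can be recovered.

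**Step 1: implied SD.** For a paired t-test, power = P(|T| > t₀.₉₇₅,₁₃), where T is noncentral t with 13 df and noncentrality 0.5·√14/SD. Setting power to 80% gives 0.5/SD = 0.810, so SD = 0.617 mm. A one-sided test would imply 0.712 mm, and every bias below would rise by 15% (0.712/0.617 = 1.15).

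**Step 2: selection model (assumed).** Write the paired difference, signed so that positive favours the screw, as

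D = δ + 0.617·(r·B + √(1−r²)·e)

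Here e is standard normal. B is the prognostic difference between the treated and untreated socket; its size is half-normal, and it favours the treated socket with probability q. The correlation r says how strongly what the operator can see predicts the outcome difference. Neither r nor q comes from the documents. Since the mean of |B| is 0.798,

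bias = 0.617 × r × 0.798 × (2q − 1).

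Example: r = 0.3, q = 0.75 gives 0.617 × 0.3 × 0.798 × 0.5 = 0.074 mm.

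**Step 3: results for n = 14, two-sided 5%, by simulation** (200,000 trials per scenario for the false-result rates, 100,000 for power). In each cell the first figure is for the favoured socket chosen 75% of the time and the second for 90%.

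| r | Size of bias (mm) | False result for the screw, better socket favoured (δ = 0) | Power for a true 0.5 mm, weaker socket favoured |
|---|---|---|---|
| 0.1 | 0.025 / 0.039 | 3.4% / 4.1% | 76.0% / 73.5% |
| 0.3 | 0.074 / 0.118 | 6.0% / 10.0% | 67.3% / 58.9% |
| 0.5 | 0.123 / 0.197 | 10.7% / 21.5% | 58.0% / 43.4% |

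With q = 0.5 (side unrelated to prognosis) the bias is zero and the false-result rate is 2.5%. As a share of the target, the bias runs from 0.025/0.5 = 5% to 0.197/0.5 = 39%.

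**Step 4: what randomising from now on would recover.** Suppose the 14 include the six completed subjects, only those six were selected, and the other eight are randomised. The bias then shrinks to 6/14 of the values above: 0.025 × 6/14 = 0.011 mm up to 0.197 × 6/14 = 0.084 mm. The false-result rate is 2.8% to 6.8%. An analysis of the eight randomised subjects alone has 50.6% power for 0.5 mm at SD 0.617 mm.

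**The case against.** The strongest reply is that silence is not evidence of non-random assignment. The text is a short research plan for a study already running under IRB approval. It refers to an approved IRB application that is not among the documents reviewed, and some front matter was not available either. The method may be stated there. This stands as a limit: the point is that the plan as supplied states no method, not that the sides were chosen badly.

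Second, the design already restrains imbalance. The sockets are contralateral maxillary premolar sites in one patient, extractions are atraumatic, and smokers and people with conditions affecting bone are excluded. The outcome is change from baseline, so a fixed difference in starting width is subtracted. These features make strong selection less likely. They do not remove selection on features that predict later loss, such as the condition of the buccal plate.

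Third, the sizes rest on assumed r and q. That is correct. The top figures need r = 0.5 and the same kind of socket picked nine times in ten. At r = 0.1 the effect is small, and a convenience or fixed-side rule unrelated to prognosis would give roughly none.

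Finally, the choice of envelopes, the avoidance of small blocks and a separate look at the randomised subjects go beyond the minimum. The essential request is random, concealed assignment and an account of the first six. The other elements are inexpensive refinements.

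**Conclusion.** The concern holds and should be fixed. The plan gives no basis for the choice of side, makes no claim of randomisation, and takes the baseline image before the choice takes effect. The primary comparison is therefore exposed to side selection that neither the blinded reading nor the planned test can remove. It also means that the smaller bone loss reported on the screw side in the six interim subjects cannot be separated from how that side was chosen.

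The possible size runs from nil, if the rule was unrelated to prognosis, to about 0.2 mm, or 39% of the 0.5 mm target, under the strongest selection considered. That conclusion assumes a two-sided test, an SD of 0.617 mm inferred from the stated power, and selection strengths chosen for illustration. That the text reviewed states no method is certain; the presence, direction and size of any actual bias are unknown.

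**What to change.** If the side has been randomised all along, state how. Otherwise, add to Section 3, item 2), wording such as:

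> For every subject not yet treated, the side is assigned by a computer-generated 1:1 left/right sequence without small blocks, prepared by someone who does not treat subjects, concealed in sealed numbered envelopes, and opened only after both extractions and the T0 CBCT.

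Small blocks are best avoided because the operator sees every past allocation. Over eight subjects, blocks of 2 make 4.0 assignments certain in advance, blocks of 4 make 2.7, and an unrestricted sequence none. The paired test does not need exact left/right balance.

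In the report, say how the side was chosen in the first six subjects and tabulate baseline width for treated and untreated sides. Show the randomised subjects separately as supportive evidence only: about 8 subjects and 51% power for 0.5 mm if the 14 include the first six, or 14 subjects and 80% if they do not.

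The cost is a protocol amendment and a set of envelopes. The sample size is unchanged and there are no extra visits. The first six cannot be re-randomised, and an analysis of about eight subjects is too weak to replace the main one.

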## **7. Research Related Risks**

Clinical risks for mini-screw are low. Overall failure rate of mini-screws is about 10% with orthodontic loading. Four to five weeks after the mini screw placement, failure rate dropped to 5%. Failures of mini-screw are mainly from loosen screws, which mean the mini-screws are mobile and are not firmly attached (or engaged) to the bone. Our incidence of loosen screws will be very low because the mini-screw will not be loaded for 6 months.

Some of the potential risks are as follows:

- Participants may experience inflammation, mild pain, or discomfort at the mini-screw site for about 2 days. Pain medication (Tylenol or Ibuprofen) will be enough to solve this problem.
- Infection rarely develops. If it occurs, antibiotics will be prescribed.
- The screw could become loose. If this occurs, the participant should contact the clinic immediately. We will remove the loosen screw and replace with a new one.
- The incidence of broken screws is very rare although a screw breaks might occur during the removal of a screw. A broken screw can be easily removed with an instrument.
- The mini-screw may not prevent bone loss.
- As with any study, there is a risk that the study data may not be kept confidential. We will minimize this risk by storing data in a secure location, such as a locked cabinet in a locked office. Electronic data will be password-protected.

**8. Potential limitation:** Not all measurements at the three levels may be significantly different. Preserving bone at the crestal and the middle level is critical in implant dentistry. Preserving bone at the apex level is clinically meaningful in orthodontics. It is difficult to measure bone loss in the palatal side with coronal sections of CBCTs. Therefore, we will also measure bone loss using axial sections of CBCTs. CT based bone density measurement may not be as accurate as direct measurement using bone biopsy. However, it is a very powerful non-invasive tool to measure mineral density.

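### No symptom recording is described between screw placement and the 3-month visit, so the zero-of-six result should not be read as absence of early inflammation

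*Combined protocol and SAP*

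**What the plan says.** Section 7 (Research Related Risks) names an early local reaction as possible: "Participants may experience inflammation, mild pain, or discomfort at the mini-screw site for about 2 days". It adds that infection is rare and would be treated with antibiotics. It gives no rate for either and no time window for infection.

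Section 3 (Research Procedures) lists the placement visit and then two later visits. The first is "3 months follow-up (30 minutes); Clinical photographs and intraoral images will be obtained for both sites". The second, headed "6 months follow-up (40 minutes", adds screw removal and a CBCT. No visit, call, diary, symptom question or inflammation score is described between placement and 3 months. Two lines under the placement visit bear on safety: "The PI and the POC will monitor subjects closely" and "Postoperative instruction will be given to subjects". Neither gives a time, a method or a form. Section 7 asks the participant to get in touch only for a loose screw: "If this occurs, the participant should contact the clinic immediately".

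Section 5 (Interim data and statistical analysis) then reports "No inflammation and infection related to the mini-screw placements were observed in all 6 subjects". It gives no assessment date or method.

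The Abstract presents the approach on the footing that "the side effects from a mini-screw placement are minimal and no antibiotics are required". The Significance and Innovation section contrasts this with grafting, after which it says inflammation and swelling are common and antibiotics are given.

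**The concern.** A reaction that resolves in about 2 days cannot be seen on photographs taken 3 months later. If no one asks about it in the first days, it enters the data only when the participant volunteers it. The plan does not say that such reports are invited or recorded. The same schedule applies to the subjects still to be treated.

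The stake is what the trial can say about tolerability. Low inflammation and no antibiotic prescription are the stated attractions of the screw over grafting, and the plan itself notes that clinical studies of this use are lacking. A reader of the final report could take a zero count as clinical confirmation when the early period was not systematically observed. Early symptoms that are not recorded at the time cannot be reliably recovered later.

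**Working it through.** The zero of six is an observed count, so there is no calculation of the plan's to reproduce. There are two separate checks: timing, and sample size.

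**Timing (from the documents)**

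- Possible early reaction: about 2 days (section 7).
- First scheduled look after placement: 3 months, about 90 days (section 3).
- Second scheduled look: 6 months (section 3). Section 5 says the screws came out at 6 months in three of the six interim subjects and at 8 months in the other three.
- Structured recording in between: none described.

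The 2-day window closes roughly 88 days before the first scheduled look (90 − 2). Persistent inflammation, or an infection still visible, could be noticed at either later visit. A transient reaction could not.

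**Sample size, assuming every event is detected**

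The exact binomial upper limit for zero events in n subjects is 1 − 0.05^(1/n) one-sided and 1 − 0.025^(1/n) two-sided.

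| Zero events in | One-sided 95% limit | Two-sided 95% limit |
|---|---|---|
| 6 (interim subjects) | 1 − 0.05^(1/6) = 39.3% | 1 − 0.025^(1/6) = 45.9% |
| 8 (remaining, if 14 includes the six) | 31.2% | 36.9% |
| 14 | 19.3% | 23.2% |

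Only the first row describes data in hand. The other two show what a zero count would mean later.

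**Effect of incomplete detection**

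Let p be the true rate and s the chance that an early event is seen. Then the probability of observing none in six is (1 − p·s)^6. The documents give neither p nor s, so these values are assumptions. With p = 30%:

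| s | Probability of 0 of 6 |
|---|---|
| 1 | (1 − 0.30)^6 = 12% |
| 0.5 | (1 − 0.15)^6 = 38% |
| 0.25 | (1 − 0.075)^6 = 63% |
| 0 | 100% |

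Put the other way, the data bound only the product p·s, at 39.3% one-sided. With s = 0.5 the limit on p becomes 0.393/0.5 = 79%. Once s falls below about 0.39, the count sets no upper limit on the early reaction rate.

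The 39% and 46% limits therefore measure how small six subjects is. The observation gap comes on top of that, and its size cannot be computed from the documents.

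**The case against.** The strongest reply has five parts.

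- **The reaction is only possible.** Section 7 lists it among potential risks, without an incidence. This is right, and nothing here assumes that it will occur.
- **The low-side-effect statements do not rest on these six subjects.** The Abstract gives them as background, and the Significance section cites a systematic review. Section 5 makes one descriptive statement and draws no conclusion from it. This also stands. A reader might infer that the gap undermines the plan's rationale, but the documents do not make that link. What is limited is what this trial's own count can add.
- **Some events would come to light.** Persistent inflammation and infection have no 2-day limit, and antibiotics prescribed by the study clinic would be known there. A reader might infer that the trial must report near-zero reactions, infections and antibiotic courses whatever the true rate. That requires detection to be nil, which the documents do not say. The supportable statement is under-counting of unknown size.
- **The plan promises close monitoring and postoperative instruction.** Both lines sit under the placement visit and have no stated content, so they do not close the gap. Early contact with the six subjects may still have taken place without being described here. That is a reason to state how they were assessed.
- **Safety is not an aim, and no planned analysis changes.** This is correct, and it keeps the point modest. It is a cheap improvement in data collection and reporting and does not touch the ridge-width comparison. Likewise, the statement that no antibiotics are needed can fairly be read as no routine prescription, so treating a rare infection does not contradict it.

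**Conclusion.** The point holds in a limited form. The plan describes no scheduled contact or symptom recording in the period when a short-lived reaction could occur, and section 5 does not say how its zero was obtained. The zero should not be read as absence of early inflammation. It is weak evidence on persistent inflammation and infection: with perfect detection it excludes only rates above 39% (one-sided) or 46% (two-sided).

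The conclusion assumes that the research plan describes all the follow-up there is. If the approved IRB application or the instructions to participants specify early contact, citing it would answer the timing part, and only the small-sample limit would remain. The figure of eight remaining subjects assumes that the planned 14 include the six already completed. If 14 more are meant, the limits for 14 apply.

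**What to change.** 1. In section 5, state when and how the six subjects were assessed for inflammation and infection, and report 0/6 with its exact upper confidence limit (39% one-sided or 46% two-sided).
2. For remaining subjects, have existing staff make one scripted call within the first days after placement. Record pain, swelling and discharge separately for each side, so that the untreated socket serves as comparator. Record analgesic and antibiotic use per participant. Ask about antibiotic use again at the 3- and 6-month visits.
3. Report the observed antibiotic-use rate with its confidence interval beside any statement from this trial that none is needed. Present the six interim subjects separately if their assessment differed.

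A further call at four to five weeks about screw looseness is a separate, optional addition and is not needed to close this gap.

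The cost is one short call per remaining subject (eight calls if 14 is the total, 14 if it is additional), one added question at two existing visits, and a wording change in section 5. Treatment, efficacy endpoint and sample size are unchanged. The downside is that the reported side-effect rate may look less favourable.

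### The planned paired t-test is not tied to one of the six width measures; the plan also gives no rule for choosing the treated side, and its 6-month label conflicts with reported 8-month removals

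*Combined protocol and SAP*

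**What the plan says.** **Test.** The whole confirmatory analysis is one sentence in Approach, item 5 (Interim data and statistical analysis): "Upon completion of the study, a paired t-test will be performed to compare the changes in the width of alveolar ridge" from the two sides.

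**Endpoint.** Approach, item 1 (Sample size determination) sets N by "considering the difference in the mean width of the edentulous alveolar ridge as the primary outcome variable". Item 4 (Radiographic Measurements) says that "three levels will be determined by measuring from the crest to the apex and dividing the socket length into thirds", and that "The measurements will be performed in coronal and axial sections". Item 8 (Potential limitation) anticipates that "Not all measurements at the three levels may be significantly different". It gives the reason for adding axial sections: "It is difficult to measure bone loss in the palatal side with coronal sections of CBCTs".

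**Interim look.** The opening of Approach says "Interim data analysis was performed from these six subjects". Item 5 reports less loss on the screw side at every level in both sections.

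**Choice of side.** Item 3 (Research Procedures) describes the step as "Placement of a mini-screw at the buccal plate of the extraction socket in one side (left or right", with no rule for which side. The baseline CBCT (T0) comes before placement. Item 4 provides for a blinded evaluator.

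**Timing.** The Abstract, Specific Aim 2 and Approach, items 3 and 4 put screw removal, the follow-up CBCT, or both at 6 months. Item 5 reports removal at 6 months in three completers and at 8 months in the other three, and attributes this to planned dental treatment.

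**The concern.** A paired t-test needs one number per side per patient. The plan produces six and does not say which of them, or which average, is the primary outcome. That leaves two routes at the end of the trial: choose a measure after seeing the data, or test all six at 5%. The first route is already partly open, because the six have been compared by side at the interim look. Either way, a significant result would not carry the 5% error rate that the sample-size statement implies.

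Two further gaps affect what the trial can conclude. Pairing removes differences between patients but not differences between the two sockets of one patient. If the treated sockets started systematically wider or narrower, and loss depends on starting width, the contrast would carry some of that difference. The plan measures T0 width but does not report it by side. In addition, a result labelled 6 months would describe a mixture of intervals.

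**Working it through.** **1. Number of measures.** 3 levels × 2 sections = 6 width changes per side (item 4). No level, section or averaging rule is stated.

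**2. The plan's sample size.** Item 1 gives N = 14, 0.5 mm and 80% power, but not the interim SD, so N cannot be reproduced. Solving backwards for a two-sided paired t-test at 5% (noncentral t, 13 df), 80% power needs a paired-difference SD of 0.617 mm, a standardized effect of 0.5 / 0.617 = 0.81. Two-sidedness is assumed, since the plan does not state it. Which of the six measures supplied the SD is not stated either.

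**3. Error rate if all six are tested.** Assumptions: each test at 5%, any one counts as success, no true effect, n = 14.
- Independent: 1 − 0.95^6 = 1 − 0.7351 = 0.2649, about 26%.
- Common correlation 0.5 (simulated): about 21%.
- Common correlation 0.9 (simulated): about 11%.

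The correlation between the measures is not in the documents. Six measures on one socket are unlikely to be independent, so 26% is an upper figure. Controlling the error by Bonferroni over six, at SD 0.617 mm, would need 22 subjects, and power at 14 would be 50%. Naming one measure keeps both 5% and N = 14.

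**4. What an unequal T0 width could do.** The T0 difference between sides, its correlation r with the difference in loss, and the paired SD are all absent from the documents, so this shows scale only. Let the mean T0 difference be k of its own SDs, and let loss truly depend on T0 width. Then bias = k × r × 0.617 mm.

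| k | r | bias (mm) | share of 0.5 mm | two-sided type I error |
|---|---|---|---|---|
| 0.5 | 0.3 | 0.5 × 0.3 × 0.617 = 0.093 | 19% | 8% |
| 0.5 | 0.5 | 0.5 × 0.5 × 0.617 = 0.154 | 31% | 14% |

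If a 0.5 SD imbalance ran against the screw, power for 0.5 mm would fall from 80% to 63% (r = 0.3) or 49% (r = 0.5). With k = 0 or r = 0 there is no bias.

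**5. Would regression on T0 width settle it?** The candidate analysis regresses the within-patient difference in width change on the within-patient T0 difference and reads off the intercept. At n = 14 with error-free T0, the slope reaches 5% significance in only 18% of simulated trials at r = 0.3 and 47% at r = 0.5. With r = 0, the mean 95% CI half-width is 0.37 mm (balanced) or 0.41 mm (0.5 SD imbalance), against 0.35 mm unadjusted. If r arises only from T0 measurement error shared with the change score, the plain t-test keeps 5% while the adjusted test rises to 14% at k = 0.5 and 28% at k = 1 (observed r = 0.5, T0-difference SD 0.5 mm). Item 4 measures change wall to wall on superimposed scans, so it is not certain that this error model applies.

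**6. Timing.** Interim mean: (3 × 6 + 3 × 8) / 6 = 7.0 months, which matches item 5. Item 4 places the CBCT after removal, so three scans labelled T6 are, by inference, no earlier than 8 months. If the six completers count toward the 14 and the rest are scanned at 6 months, 3/14 = 21% are 8-month cases and the mean is (3 × 8 + 11 × 6) / 14 = 6.4 months. If half of all 14 reach 8 months, the mean is 7.0.

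**The case against.** The strongest reply is that most of this is conditional. Item 5 speaks of a single paired t-test, and item 1's mean width may be intended as an average. Nothing says that six tests will be run or that any one would count as success. Item 8 also gives the levels different clinical purposes. This limits the familywise figures to a what-if. It does not answer the point that the plan fixes no level, section or average.

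On side choice, a reader might infer that the comparison is confounded by T0 width and that a baseline-adjusted analysis is required. The documents do not support this. They report no T0 difference and no dependence of loss on T0 width. A change score already removes a purely additive difference. At n = 14 the regression is imprecise and can itself be biased. A side-selection rule may also stand in the separate IRB application that item 3 mentions and that is not available here. The blinded evaluator protects the measurement but has no bearing on which side was treated.

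On timing, a reader might infer that mixed intervals bias the result. They do not, because both sockets of a patient share one interval. The late removals are disclosed with a reason, and the Significance section puts most bone loss in the first 3 months, so the numerical effect may be small.

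**Conclusion.** The concern holds as a correction that should be made. The part that rests on the text alone is the unnamed endpoint: six candidate measures, all already seen by side. The cost of leaving it open is a false-positive rate of about 11% to 26% if all six are tested and any one suffices, depending on an unknown correlation, or a post-hoc choice whose error rate cannot be stated.

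The missing rule for side choice is a real gap, but of unknown consequence. A T0 difference cannot be excluded because the scan precedes placement, and none is shown. The 8% to 14% error rates above rest entirely on assumed values of k and r and on the back-solved SD. The 6- versus 8-month conflict concerns which time point the conclusion describes. The 8-month scan dates are inferred from the removal dates.

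**What to change.** 1. **Endpoint.** Keep the paired t-test as primary and apply it to one named measure, for example the average over the three levels in one stated section. Make the choice on clinical and measurement grounds, date it as post-interim, and report the other measures as secondary. State the SD behind N = 14 and the measure it came from. The 80% power holds only if the named measure has that SD (about 0.62 mm if two-sided).
2. **Side.** For subjects not yet treated, choose the side at random. For the others, state how it was chosen. Report T0 width by treated and untreated side, with the mean and SD of the within-patient difference. A regression on that difference is at most an optional exploratory estimate, labelled as imprecise and open to bias from T0 measurement error.
3. **Timing.** Reconcile the 6-month statements in the Abstract, Specific Aim 2 and Approach, items 3 and 4 with the removals reported in item 5. Record months from placement to scan for each subject, and label the endpoint by the actual interval and range.

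**Cost.** Some SAP wording, a randomization step for the remaining subjects, one small table and one interval per subject, all from scans already planned. The investigators lose the freedom to choose among six measures, and an average could dilute an effect confined to one level. Dating the choice makes the interim look visible but does not undo it, and random choice of side cannot repair the sides already chosen.
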